11.3 VITAL SIGNS

Descriptive statistics for vital signs (systolic and diastolic blood pressure, pulse rate, temperature and body weight) and changes from baseline values at each visit and at the end of study will be presented by treatment group.

Vital sign values will be considered PCS if they meet both the observed-value criteria and the change-from-baseline criteria listed in Table 11.3–1. The number and percentage of participants with PCS postbaseline values will be tabulated by treatment group. The percentages will be calculated relative to the number of participants with available non-PCS baseline values and at least 1 postbaseline assessment. The numerator will be the total number of participants with available non-PCS baseline values and at least 1 PCS postbaseline value. A supportive listing of participants with PCS postbaseline values will be provided, including the PID number, baseline and all postbaseline (including non-PCS) values.

Table 11.3–1. Criteria for Potentially Clinically Significant Vital Signs

Parameter	Flag	Criteria^a	
		Observed Value	Change From Baseline
Sitting systolic blood pressure, mm Hg	High	≥ 150	Increase of ≥ 20
	Low	< 90	Decrease of ≥ 20
Sitting diastolic blood pressure, mm Hg	High	≥ 100	Increase of ≥ 15
	Low	< 50	Decrease of ≥ 15
Sitting pulse rate, bpm	High	≥ 100	Increase of ≥ 15
	Low	< 50	Decrease of ≥ 15
Weight, kg	High	—	Increase of ≥ 7%
	Low	—	Decrease of ≥ 7%

a A postbaseline value is considered potentially clinically significant if it meets both the observed-value and the change-from-baseline criteria.

bpm = beats per minute.

11.4 OTHER SAFETY PARAMETERS

11.4.1 Physical Examination

Physical examination will be performed at screening and at study exit visit. All findings at the screening visit will be recorded on the Medical and Surgical History/Physical Findings eCRF page. Any new or worsening condition observed at the study exit visit will be recorded on the Adverse Event eCRF page. Hence summaries for physical examinations will be captured in summaries presented for medical and surgical history and adverse events.

11.4.2 Post-Void Residual Urine Volume

Descriptive statistics for PVR urine volume (mL) and changes from baseline values at each visit and at the end of study will be presented by treatment group. In addition, the number and percentage of participants with PVR urine volume within each of the following categories will be presented by treatment group for each postbaseline visit as well as for the entire study:

- < 100 mL
- \geq 100 mL and < 200 mL
- \geq 200 mL and < 350 mL
- \geq 350 mL

11.4.3 Bladder and Kidney Ultrasound

A listing of all participants with at least one pre-existing or new bladder or kidney condition will be provided for the Safety Population by treatment group.

11.4.4 Concurrent Procedures

Concurrent procedures will be presented in a listing together with the indication for which the procedure was performed. The indication will be coded using MedDRA system organ class and preferred term.

11.4.5 Catheterization Use

The number and proportion of participants catheterizing will be summarized, broken out by reason (for urinary retention or for other reasons) and whether it was CIC or not. This will be determined from the Catheterization eCRF. For the participants who initiate CIC for urinary retention post-instillation, the average number of catheterization urinary episodes per day will be calculated based on the bladder diary. These will be summarized by treatment group with descriptive statistics. The total duration of CIC usage for participants who do so for urinary retention post-instillation will be determined from the Catheterization eCRF and summarized using descriptive statistics by treatment group.

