The dose-finding study (Study 191622-077) evaluated a range of BOTOX doses (50 U, 100 U, 150 U, 200 U, and 300 U) versus placebo (N = 313). The phase 3 program included 2 identical pivotal phase 3 studies in OAB patients who were not adequately managed with anticholinergic therapy (Study 191622-095, N = 557 and Study 191622-520, N = 548). Patients in both studies received 100 U BOTOX or placebo administered as intradetrusor injections via cystoscopy. Patients could receive an additional treatment of 100 U BOTOX if pre-specified retreatment criteria were fulfilled and could enter a long-term extension study (Study 191622-096, 3 years duration) in which they could receive multiple treatments of BOTOX (100 U or 150 U BOTOX). Both pivotal phase 3 studies achieved both co-primary efficacy endpoints of significant reductions in urinary incontinence at Week 12 and a significantly higher proportion of patients reporting their condition as improved or greatly improved on the Treatment Benefit Scale (TBS) (Nitti 2013a; Chapple 2013). In addition, all secondary endpoints were met in both pivotal studies, which included OAB symptoms and other HRQL parameters. The duration of effect of BOTOX, based on the first 100 U BOTOX treatment cycle phase 3 data integrated with the long-term extension study data, was approximately 6 months.

With respect to safety, adverse events were primarily local adverse events related to the urinary tract, in particular, urinary retention and UTI. Treatment with 100 U BOTOX was associated with a transient increase in PVR urine volume with a peak effect by Week 2, although majority of the patients did not have an increase greater than 100 mL.

A consistent efficacy and safety profile has been demonstrated with repeat BOTOX treatment with peak efficacy between Week 6 and Week 12 post injection. The reductions from baseline in urinary incontinence episodes remained similar over repeated BOTOX treatments, as did the improvement in HRQL. The most common adverse events remained urological (eg, UTI and urinary retention), and the incidence of such adverse events did not increase with repeated BOTOX treatment.

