#### **9.4.5. Clean Intermittent Catheterization**

The following guidance should be used for the initiation of CIC in this study. Sterile, single use intermittent catheters should be used. Indwelling catheters should not be used in this study.

**BOTOX® (Botulinum Toxin Type A)  
Purified Neurotoxin Complex***Initiation of Clean Intermittent Catheterization*

As described above in the [PVR section](#), CIC should be initiated per protocol when one of the following criteria is fulfilled:

- PVR is  $\geq 350$  mL at any posttreatment visit, regardless of whether the participant reports associated symptoms
- PVR is  $\geq 200$  mL and  $< 350$  mL and the participant spontaneously reports associated symptoms (ie, voiding difficulties, sensation of bladder fullness) that in the opinion of the investigator requires CIC.

The following will occur when initiating CIC (for elevated PVR as described above):

1. CIC is implemented and the participant should be instructed to perform CIC using sterile, single-use catheters (which will be provided to the participant)
2. An adverse event of urinary retention is recorded
3. Central laboratory urine analysis and culture/sensitivity are performed as per routine requirements at each study visit
4. The participant will be seen for a follow-up visit 1 week later where the PVR, associated symptoms, central laboratory urine analysis and culture/sensitivity will be reassessed. The investigator will determine whether the participant can then be followed per protocol scheduled study visits or whether additional follow-up visits should occur.

Once CIC is initiated, the status of CIC use should be documented in the participant record at each visit (ie, use/nonuse).

*Cessation of Clean Intermittent Catheterization*

CIC should be discontinued when the following criteria are fulfilled:

- the participant does not have any associated symptoms which in the opinion of the investigator require CIC AND
- the PVR is  $< 350$  mL

The date of discontinuation of CIC should be documented. If the investigator deems that CIC should not be discontinued even though the above criteria are fulfilled, then this should be documented and the reason given. Upon discontinuing CIC the participant will be seen for a follow-up visit 1 week later where the PVR, associated symptoms, central laboratory urine

**BOTOX® (Botulinum Toxin Type A)  
Purified Neurotoxin Complex**

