Within each cohort, participants will be randomized in a 4:1 ratio to receive either BOTOX or placebo. A total of 50 to 70 participants will be randomized to receive study treatment in Stage 1 ([Figure 4-1](#)).

[figure not shown]
The analyses will consider up to 5 treatment groups, BOTOX 100 U, 300 U, 400 U, 500 U, and Placebo. In all analyses, data from the Placebo treatment group will be pooled across all cohorts in Stage 1 of the study.

The total duration of each participant's planned participation is 14 weeks, including a 2-week screening and 12-week treatment/follow-up period. The screening period can be extended by an additional 2 weeks in cases where a participant has a positive urine dipstick at the scheduled Day 1 visit. The schedule of activities is presented in [Table 4-1](#).

Figure 4-1

Schematic of Stage 1 Study Design

5.0 **OBJECTIVES**

The objective of Stage 1 of this study is to compare the safety of a single treatment of BOTOX intravesical instillation, with possible doses ranging from 100 U up to 500 U, with placebo in participants with OAB and urinary incontinence. A limited exploratory analysis is also being performed on select efficacy endpoints.

[figure not shown]

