13.0 DETERMINATION OF SAMPLE SIZE

For Stage 1, approximately 50 to 70 participants will be enrolled to ensure that 10 to 20 individuals are randomized into each of the 4 cohorts (100 U Cohort: n = 10; 300 U Cohort: n = 20; 400 U Cohort: n = 20; 500 U Cohort: n = 20) to provide sufficient data in the analysis and interpretation of safety results. Two adverse events of particular interest are urinary retention and urinary tract infection (UTI). From previous BOTOX studies, the percentage of participants in the BOTOX-treated population experiencing these adverse events is approximately 6% to 7% for urinary retention and 20% to 30% for UTI. In Cohort 1, the probability of observing at least one BOTOX-treated participant experiencing these adverse events is 0.39 to 0.44 and 0.83 to 0.94, respectively. For the other cohorts, the probability of observing at least one BOTOX-treated participant experiencing these adverse events is 0.63 to 0.69 and 0.97 to ~ 1, respectively.

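### Stage 1 SAP 11.4.5 gives no rule for CIC still ongoing at Week 12 or exit, so the planned descriptive summary of CIC duration can understate it by an unknown amount

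*SAP*

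**What the plan says.** Stage 1 SAP 11.4.5 has an incidence part and a duration part. For incidence, "The number and proportion of participants catheterizing will be summarized, broken out by reason" and by whether the catheterization was CIC. The duration part covers "The total duration of CIC usage for participants who do so for urinary retention post-instillation", and this "will be determined from the Catheterization eCRF and summarized using descriptive statistics by treatment group". Section 11.0 of the same SAP defines descriptive statistics for a continuous safety variable: number of participants, mean, SD, median, quartiles, minimum and maximum.

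Stage 1 SAP 4.0 sets planned participation at 14 weeks, "including a 2-week screening and 12-week treatment/follow-up period". Protocol 9.4.5 adds that "The date of discontinuation of CIC should be documented", and that CIC use or non-use is noted at each visit once CIC has begun.

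The date-handling rules do not fill the gap. Section 15.7 deals with adverse event start dates and 15.8 with medication dates. Section 15.2 has no visible text in the public copy, but its title concerns diary data, whereas CIC duration comes from the eCRF.

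Section 13.0 names urinary retention as one of two adverse events of particular interest and gives the rates from earlier studies as "approximately 6% to 7% for urinary retention and 20% to 30% for UTI".

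**The concern.** A stop date exists only once CIC has stopped. For a participant still catheterizing at Week 12, or at an earlier exit, the true duration is known only to exceed the observed time. Mean, SD and quartiles treat every value as complete. If the missing stop date removes the participant, the longest durations leave the table. If the exit date is used as the stop date, the longest durations are shortened. In both cases the mean is biased downward, and the bias grows with the true duration.

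Stage 1 exists to describe safety by dose. In the visible text this is the only display of how long participants at each dose needed CIC, since the catheterization section of the Stage 2 SAP plans no duration summary. The Stage 1 figures may therefore be read as the CIC burden at each dose.

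**Working it through.** **1. The plan's own figures.** Protocol 7.1.1 gives 8 BOTOX participants in the 100 U cohort and 16 in each higher cohort. The probability of at least one retention event is 1 − (1 − p)^n.

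- n = 8: 1 − 0.94^8 = 0.390 and 1 − 0.93^8 = 0.440. The plan states 0.39 to 0.44.
- n = 16: 1 − 0.94^16 = 0.628 and 1 − 0.93^16 = 0.687. The plan states 0.63 to 0.69.

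Both ranges reproduce.

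**2. How many CIC users to expect.** Protocol 9.2.6 defines the retention event by the need for CIC, so the retention rate serves as the CIC rate.

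- 100 U arm: 8 × 0.06 to 8 × 0.07 = 0.48 to 0.56.
- Each 16-person arm: 16 × 0.06 to 16 × 0.07 = 0.96 to 1.12. The chance of no user is 31% to 37%, and of two or more 25% to 31%.
- All BOTOX participants: 8 + 16 + 16 = 40 with three cohorts, or 56 with four. This gives 40 × 0.06 = 2.4 to 56 × 0.07 = 3.9.

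**3. How long CIC can be observed.** Stage 1 SAP Table 15.1-1 puts Week 2 at Day 15, Week 6 at Day 43 and Week 12 at Day 85. CIC begun at Week 2 is seen for at most 85 − 15 = 70 days, or 10 weeks. CIC begun at Week 6 is seen for at most 42 days, or 6 weeks.

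**4. Direction and possible size of the bias.** The documents give no distribution for CIC duration. As an assumption, take exponential durations with true mean m weeks and an observation window of C weeks.

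- Share still on CIC at exit: exp(−C/m).
- Mean if ended at exit: m(1 − exp(−C/m)).
- Mean if ongoing cases are left out: m − C·exp(−C/m)/(1 − exp(−C/m)).

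| Start | True mean (wk) | Ongoing at exit | Mean if ended at exit (wk) | Mean if left out (wk) |
|---|---|---|---|---|
| Week 2 (C = 10) | 6 | 19% | 4.9 | 3.7 |
| Week 2 | 12 | 43% | 6.8 | 4.3 |
| Week 2 | 24 | 66% | 8.2 | 4.7 |
| Week 6 (C = 6) | 6 | 37% | 3.8 | 2.5 |
| Week 6 | 12 | 61% | 4.7 | 2.8 |
| Week 6 | 24 | 78% | 5.3 | 2.9 |

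For a Week 2 start, the mean is 19%, 43% and 66% too short if cases are ended at exit, and 39%, 64% and 81% too short if they are left out. The median is less exposed. With a common Week 2 start and cases ended at exit, it stays correct while fewer than half are ongoing: 4.2 and 8.3 weeks for true means of 6 and 12. At a true mean of 24 weeks the true median of 16.6 weeks would read as 10.

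**5. What this means in very small arms.** Suppose an arm has two CIC users, one with complete duration d and one still on CIC after 10 weeks. Leaving out the ongoing case gives a mean of d, and ending it at exit gives (d + 10)/2. The true mean is at least (d + 10)/2. With one user who is ongoing, the first rule gives no value and the second gives 10 weeks whatever the true duration. The unstated rule then decides what is reported.

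**The case against.** The strongest reply is that the SAP is silent rather than wrong. Table and listing specifications are in a separate document that is not public, and a convention for ongoing CIC may be there. The data should largely exist: starting CIC triggers a retention adverse event (Protocol 9.4.5), the need to catheterize helps to set its stop date (9.2.6), adverse events are followed to resolution or stabilization (9.2.3), and CIC status is noted at each visit. This stands as far as it goes: the handling is unknown, not shown to be biased. It does not close the gap. Protocol 9.2.1 collects adverse events only up to the last follow-up visit, and the SAP takes duration from the Catheterization eCRF, so a stop date after exit may never reach the table.

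The table would also give some warning. If ongoing users were left out, the number of participants behind the duration would fall below the count of CIC users in the same section. If they were ended at exit, the maximum would lie near the follow-up limit. Post-void residual (PVR) categories by visit, adverse event severity and the diary listings add context. All of this stands, but none of it replaces a statement of which durations are incomplete.

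The long durations in the working are assumptions. Protocol 3.2.4 reports that the effect of the first 100 U injection cycle, from "phase 3 data integrated with the long-term extension study data, was approximately 6 months", but that is duration of benefit after injection, not of CIC after instillation. The same section describes a "transient increase in PVR urine volume with a peak effect by Week 2" and says that most patients rose by no more than 100 mL. An exponential mean of 24 weeks leaves exp(−1) = 37% on CIC beyond 24 weeks, which is an extreme case.

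A reader might infer that the doses with the longest retention will look almost as benign as the others. The documents do not support this. It is approached only if ongoing cases are left out and true durations are long: true means of 6 and 24 weeks would then show as 3.7 and 4.7. If cases are ended at exit, 4.9 against 8.2 weeks remains, a 1.7-fold difference. No document suggests a fourfold difference between doses, and with about one user per arm, small numbers limit any dose contrast more than censoring does.

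**Conclusion.** The point holds as a gap in the Stage 1 plan. CIC duration is right-censored at Week 12 or exit, the planned statistics treat it as complete, and no visible rule covers ongoing use. Under either usual handling the mean is understated, more so where CIC lasts longer.

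The size is unknown. The percentages in the working rest on assumed exponential durations and assumed start weeks. The expected 2 to 4 CIC users rest on the planning rate of 6% to 7% carrying over to instillation at every dose. With so few users, the practical risk is that one ongoing case determines an arm's reported mean, rather than a systematic distortion across doses.

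The consequence is limited to how CIC burden is reported. Under Stage 1 SAP 12.0, escalation and the choice of Stage 2 doses rest on the data review committee's review of unblinded safety data at Week 6, not on this table.

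**What to change.** Amend Stage 1 SAP 11.4.5 to:

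1. Report, by dose, the number of participants using CIC for urinary retention who are still on CIC at study exit, next to the number who used it.
2. List each such participant's CIC start, stop or last-known date and duration, with a plus sign where CIC was ongoing and the duration is therefore censored.
3. Give no mean that mixes complete and censored durations. Add a Kaplan-Meier median only if an arm has enough CIC users to support one.
4. State whether a stop date learned after exit, for example through adverse event follow-up, may be used.

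The cost is a few lines of SAP text and programming. No new data are needed, because CIC status is already documented at each visit. The small downside is that some doses will have no single summary duration. With about one user expected per arm, the listing carries nearly all the information.

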12.0 INTERIM ANALYSIS

No formal interim analysis is planned for this study. However, an independent data review committee (DRC) will review unblinded safety data from Stage 1 upon completion of the Week 6 post-instillation follow-up time point from each cohort. Based on the observed safety data from these reviews, the DRC will recommend to proceed with dose escalation from one cohort to the next. In addition, after review of the safety data in the 100 U and 300 U Cohorts, the DRC will recommend to proceed with dose escalation either to BOTOX 400 U followed by BOTOX 500 U or whether it is safe to proceed directly to BOTOX 500 U.

The DRC will also recommend to proceed with Stage 2 of the study and recommended the doses of BOTOX intravesical instillation for further investigation during Stage 2 based on an unblinded review of the safety data after completion of the Week 6 post-instillation follow-up time point of the 500 U Cohort in Stage 1 (stage 2 BOTOX doses will be 100 U, 300 U, 400 U and either a 500 U or a 200 U dose group).

If further safety data is required by the DRC prior to proceeding with dose escalation from one cohort (or stage) to the next, additional participants may be enrolled into a cohort as recommended by the DRC.

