treatment groups, including 4 BOTOX arms and 1 placebo arm. Participants who receive study treatment in Stage 1 are not eligible to enroll in Stage 2.

- At Day 1, participants in both Stage 1 and Stage 2 will be randomized centrally to receive either a single treatment of BOTOX or matching placebo via intravesical instillation. Randomization will be stratified by baseline urgency urinary incontinence episodes and sex for Stage 2 only.
- In Stage 1, participants will be randomized in a 4:1 ratio to receive either BOTOX (100 U, 300 U, 400 U [optional], 500 U) or placebo. For each cohort in Stage 1, an unblinded safety review by the DRC will be performed when all participants reach Week 6. Enrollment into the next cohort at the higher dose will begin only after the DRC has deemed it safe to proceed to the next cohort.
- In Stage 2, participants will be randomized in a 1:1:1:1:1 ratio for treatment with either BOTOX 100 U, BOTOX 300 U, BOTOX 400 U, BOTOX 500 U (or 200 U), or placebo.
- Confirmation of the BOTOX doses for investigation in Stage 2 will occur after review of unblinded safety data from the 500 U Cohort in Stage 1 by the DRC. Based on this review, the DRC will have the option to replace the BOTOX 500 U treatment group with BOTOX 200 U in Stage 2.

• Visit Schedule:

BOTOX® (Botulinum Toxin Type A)  
Purified Neurotoxin Complex

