## 5. Study Design

### 5.1. Overall Design

This is a multicenter, randomized, double-blind, placebo-controlled, single-treatment, 2-stage, dose-finding study. The total duration of participant participation in Stage 1 is 14 weeks, including a 2-week screening and 12-week treatment/follow-up period. Total duration of participation in Stage 2 is 28 weeks, including a 4-week screening and 24-week treatment/follow-up period.

For Stage 1, BOTOX intravesical instillation doses (100 U, 300 U, [400 U], 500 U) will be investigated in 3 or 4 consecutive cohorts (Figure 5-1). Upon completion of the Week 6 post instillation follow-up timepoint, safety data from each cohort will be reviewed by an independent data review committee (DRC) prior to starting enrollment into the next dose cohort. Based on the observed safety data from the 100 U and 300 U Cohorts, the DRC will recommend to proceed with either BOTOX 400 U followed by BOTOX 500 U or whether it is safe to dose escalate directly to BOTOX 500 U. Each cohort will be randomized in a 4:1 ratio to receive BOTOX or placebo.

Stage 2 will investigate 4 doses of BOTOX (100 U, 300 U, 400 U, 500 U [or 200 U]) compared to placebo in a 1:1:1:1 ratio. Depending on the outcome of DRC review of safety results from the 500 U Cohort in Stage 1, BOTOX 500 U may be replaced with a BOTOX 200 U treatment group (Figure 5-1).

[figure not shown]
BOTOX or placebo in a Hydrogel admixture will be instilled into the bladder as a single intravesical instillation through a sterile, single use catheter using aseptic technique per local site practice. The total volume to be instilled will be 60 mL.

The primary efficacy measure will be the number of urinary incontinence episodes per day recorded on a 3-day participant bladder diary. Key secondary response measures will be the number of micturition episodes per day and the volume voided per micturition to be recorded on a 3-day participant bladder diary. Additional measures in Stage 2 will include urodynamic parameters

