### 5.1.1. Data Review Committee

An independent DRC will review unblinded safety data from Stage 1, upon completion of the Week 6 post-instillation follow-up time point from each cohort. Based on the observed safety data from these reviews, the DRC will recommend to proceed with dose escalation from one cohort to the next. In addition, after review of the safety data in the 100 U and 300 U Cohorts,

**BOTOX® (Botulinum Toxin Type A)  
Purified Neurotoxin Complex**

the DRC will recommend to proceed with dose escalation either to BOTOX 400 U followed by BOTOX 500 U or whether it is safe to proceed directly to BOTOX 500 U.

The DRC will also recommend to proceed with Stage 2 and select the doses of BOTOX intravesical instillation for further investigation during Stage 2 based on unblinded review of the safety data from the 500 U Cohort in Stage 1.

If additional safety data are required by the DRC prior to proceeding with dose escalation from one cohort (or stage) to the next, additional participants may be enrolled into a cohort as recommended by the DRC.

The DRC will remain in place throughout Stage 2 of the study.

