**Stage 2**

- 100 U BOTOX intravesical instillation (BOTOX and Hydrogel admixture) (n = 53)
- 300 U BOTOX intravesical instillation (BOTOX and Hydrogel admixture) (n = 53)
- 400 U BOTOX intravesical instillation (BOTOX and Hydrogel admixture) (n = 53)
- 500 U (option to replace with 200 U) BOTOX intravesical instillation (BOTOX and Hydrogel admixture) (n = 53)
- BOTOX Placebo intravesical instillation (Placebo and Hydrogel admixture) (n = 53)

The four BOTOX doses for investigation in Stage 2 will be selected based on the review of unblinded safety data from the 500 U Cohort in Stage 1 by the DRC. The DRC will have the option to replace the 500 U treatment group with BOTOX 200 U in Stage 2.

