4.0 INTRODUCTION

This statistical analysis plan (SAP) provides a more technical and detailed elaboration of the statistical analyses of the efficacy and safety data specified in the [final protocol](#) of Study 1839-201-021 (version dated 8 June 2017) and the most recent amendment ([amendment 2](#) dated 20 Dec 2018). Specifications of tables, figures, and data listings are contained in a separate document. There are two stages in this study. This SAP is for Stage 2 of the study. The SAP for Stage 1 of the study will be prepared in a separate document. Stage 1 and Stage 2 data will be analyzed separately. In addition, adverse event data for the first 12 weeks (84 days) from each stage of the study will be pooled.

[figure not shown]
This study is a phase 2, multicenter, randomized, double-blind, placebo-controlled, single-treatment, 2-stage, dose-finding study for participants with overactive bladder (OAB) and urinary incontinence who are inadequately managed by pharmacologic therapies. The 2-stage study design allows for an assessment of safety during Stage 1 in a conservative, placebo-controlled dose-escalating manner prior to the initiation of Stage 2 where the efficacy and safety of BOTOX instillation will be evaluated in a placebo-controlled, parallel group, dose-finding design.

Total duration of participation in Stage 2 is 28 weeks, including a 4-week screening and 24-week treatment/follow-up period. The schedule of activities is presented in [Table 4-1](#).

Stage 2 will investigate 4 doses of BOTOX (100 U, 300 U, 400 U, 500 U [or 200 U]) compared to placebo in a 1:1:1:1:1 ratio. A total of 265 randomized participants are required for Stage 2. Depending on the outcome of Data review committee (DRC) review of safety results from the 500 U Cohort in Stage 1, BOTOX 500 U may be replaced with a BOTOX 200 U treatment group (Figure 4-1).

BOTOX or placebo in a Hydrogel admixture will be instilled into the bladder as a single intravesical instillation through a sterile, single use catheter using aseptic technique per local site practice. The total volume to be instilled will be 60 mL.

Figure 4-1 Study Design Diagram

[figure not shown]

Stage 2 will begin after confirmation of the 4 BOTOX doses for investigation in Stage 2 based on unblinded review of safety results from the 500 U Cohort in Stage 1 by the DRC

CONFIDENTIAL

BOTOX® (Botulinum Toxin Type A)
Purified Neurotoxin Complex

[figure not shown]
Page 7

CONFIDENTIAL

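### Does the plan leave the Stage 2 400 U arm unguarded if its optional Stage 1 cohort is skipped and 500 U is then replaced?

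*SAP*

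**What the plan says.** **Stage 1.** Protocol 7.1.1 marks the 400 U cohort as optional. After the 300 U review the DRC recommends either 400 U followed by 500 U, or 500 U directly (Protocol 5.1 and 5.1.1; Stage 1 SAP 12.0).

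**Stage 2 dose lists.** The lists carry 400 U without condition. Stage 2 SAP 4.0: "Stage 2 will investigate 4 doses of BOTOX (100 U, 300 U, 400 U, 500 U [or 200 U]) compared to placebo". Stage 1 SAP 12.0: "stage 2 BOTOX doses will be 100 U, 300 U, 400 U and either a 500 U or a 200 U dose group". The one substitution named is at the top dose. Protocol 5.1, on the outcome of the 500 U review: "BOTOX 500 U may be replaced with a BOTOX 200 U treatment group". Protocol 7.1.1: "The DRC will have the option to replace the 500 U treatment group with BOTOX 200 U in Stage 2".

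**DRC remit.** Protocol 5.1.1 has the DRC recommend whether to proceed to Stage 2 and "select the doses of BOTOX intravesical instillation for further investigation during Stage 2". Protocol 7.1.1, under the dose list itself: "The four BOTOX doses for investigation in Stage 2 will be selected based on the review of unblinded safety data". Footnote b to the design description in the Synopsis, and the note to Figure 4-1 in the Stage 2 SAP, make the start of Stage 2 wait for confirmation of all four BOTOX doses. If the DRC wants more safety data before the next cohort or stage, "additional participants may be enrolled into a cohort as recommended by the DRC". Protocol 5.1.1 also keeps the committee in place for the whole of Stage 2.

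**The concern.** Protocol 5.4 presents Stage 1 as a cautious, escalating safety assessment that comes before the parallel-group stage. The lists appear to break that sequence on one route. If 400 U is skipped and 500 U is then judged unsuitable, applying the lists literally puts a full arm on 400 U. That dose would have no Stage 1 data of its own, would lie above 300 U, and would be the top dose just after the next higher one had been replaced on safety grounds. The 200 U substitute also has no Stage 1 cohort, but it lies below 300 U.

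The wording adds to the doubt. Some sections let the DRC choose the doses, while the lists name only the exchange of 500 U for 200 U. A reader could conclude that the committee has no say over 400 U. What would be at stake is the safety of one fifth of the Stage 2 participants.

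**Working it through.** **Inputs** (Protocol 7.1.1 and 10.1; Stage 1 SAP 13.0). BOTOX + placebo per cohort: 8 + 2 at 100 U; 16 + 4 at each of 300, 400 (optional) and 500 U. Stage 2: 53 per arm, five arms. Assumed event rates: urinary retention 6% to 7%, UTI 20% to 30%.

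**The plan's own figures.** The chance of at least one event among n treated is 1 − (1 − p)^n.

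- n = 8, retention: 1 − 0.94^8 = 0.39 and 1 − 0.93^8 = 0.44. UTI: 1 − 0.80^8 = 0.83 and 1 − 0.70^8 = 0.94.
- n = 16, retention: 1 − 0.94^16 = 0.63 and 1 − 0.93^16 = 0.69. UTI: 1 − 0.80^16 = 0.97 and 1 − 0.70^16 = 0.997.

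All match the stated values.

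**Skipping 400 U is a planned path.** Stage 1 total without it: 10 + 20 + 20 = 50. With it: 10 + 20 + 20 + 20 = 70. These are the two ends of the stated range. BOTOX-treated without it: 8 + 16 + 16 = 40.

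**The four routes.**

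| 400 U cohort | 500 U in Stage 2 | Treated at 400 U in Stage 1 | Top listed Stage 2 dose |
|---|---|---|---|
| run | kept | 16 | 500 U |
| run | replaced | 16 | 400 U |
| skipped | kept | 0 | 500 U |
| skipped | replaced | 0 | 400 U |

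Only the last row raises the question. There, 53/265 = 0.20 of Stage 2 is assigned to 400 U, and the 0.63 to 0.69 chance of seeing a retention event has no counterpart at that dose.

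**What the DRC would hold on that row.** It would have unblinded data through Week 6 from 16 treated at 300 U and 16 at 500 U, so 16 + 16 = 32 of the 40 treated participants received a dose on one side or the other of 400 U. To reach this row the committee must already have judged, after the 300 U review, that going directly to 500 U was safe.

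**Lists against remit.** Protocol 7.1.1 prints the list, the statement that the four doses are selected on DRC review, and the 500-to-200 U option together. They fit as a default list, subject to DRC confirmation, with one substitute named in advance. The Stage 1 SAP parenthesis is the tightest wording, but it sits inside the sentence that has the DRC recommend the Stage 2 doses. Under the Synopsis, sites are told that Stage 2 enrollment may begin only after the 500 U review. The decision on 400 U therefore comes before anyone is randomized to it.

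**Effect on the analysis.** None. With 50 per group, a difference of 1.8 and an SD of 3.5, the two-sample t-test has power 0.721, against the stated 72%. Stage 2 SAP 10.1 compares each BOTOX group with placebo. Neither depends on which Stage 1 cohorts were run.

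**The case for a change.** The strongest reply is that the DRC's powers permit action without requiring it. No section ties the 400 U arm to its Stage 1 cohort, no substitute for 400 U is named, and the text does not say whether a skipped cohort could be opened late. Having 16 participants at 500 U does not clear 400 U if 500 U has just been replaced on safety grounds. The earlier overactive bladder and neurogenic experience with intradetrusor injection that Protocol 5.5 cites stops at 300 U.

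Much of this stands as description. The documents are silent on this branch, and the Stage 1 SAP parenthesis reads as more closed than Protocol 5.1.1. It does not follow that the plan fails there. Adverse 500 U results neither clear nor condemn 400 U, but they are the evidence an unblinded independent committee would weigh before confirming the four doses. Leaving that judgment to the committee instead of scripting each branch is a normal trade-off in a dose-escalation design. The missing 0.63 to 0.69 illustrates what a cohort of that size can show; the plan does not use it as a clearance criterion.

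**Conclusion.** No change follows. The gap is real but narrow: one of four routes, on which 53 of 265 participants (20%) would be assigned to a dose with no Stage 1 participants of its own. A mandatory DRC confirmation covering all four doses precedes any Stage 2 enrollment, and the committee can ask for more data first. Following the plan with that gate is not shown to give a wrong result, and no sample size, power figure or analysis moves.

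This rests on reading the dose lists as defaults subject to that confirmation, which the Synopsis footnote and Protocol 5.1.1 and 7.1.1 support. It also rests on the text alone: the design schematics are not available here, and the documents do not show which route was taken. The count of routes says nothing about how likely each is. Nothing here is a view on which dose is appropriate.
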